11.3.3 Analysis of the Primary Endpoint

The data will be collected and electronically transferred to the core laboratory at the University of Illinois, Chicago, IL, where [name], PhD, will analyze data at the end of the study. After locking the database, he will be provided a group allocation according to treatment A or B (blinded to real treatment). The data will be analyzed according to blinded group allocation and the description of the group allocation will be disclosed only after completion of the analysis. The differences in interval changes between the treatments will be compared using random-effect analysis of variance for repeated measures to analyze the effects of time and group allocation. Unadjusted p values will be reported throughout, with statistical significance set at the 2-tailed 0.05 level. All analyses will be based on a 'complete case' approach.

DSMB CHARTER**Charter, Data and Safety Monitoring Board for**

NHLBI 1R34HL118348-01A1

Interleukin-1 blockade in heart failure with preserved ejection fraction:

REcently Decompensate Heart failure Anakinra Response Trial -2

(REDHART2)

Updated on October 25, 2018

DSMB Liaison: [name] – [contact]

1 Introduction

This Charter is for the Data and Safety Monitoring Board (DSMB) for the study: **Interleukin-1 blockade in recently decompensated heart failure: the REcently Decompensated Heart failure Anakinra Response Trial-2 (REDHART2)**, hereafter referred to as “REDHART2”.

The Charter is intended to be a living document. The DSMB may wish to review it at regular intervals to determine whether any changes in procedure are needed.

2 Responsibilities of the DSMB

The DSMB is responsible for safeguarding the interests of study participants, assessing the safety and efficacy of study procedures, and for monitoring the overall conduct of **REDHART2**.

The DSMB is an independent group advisory to the investigators, and is required to provide recommendations about starting, continuing, and stopping the study **REDHART2**. In addition, the DSMB is asked to make recommendations, as appropriate, to the investigators about:

- Participant safety
- Benefit/risk ratio of procedures and participant burden
- Selection, recruitment, and retention of participants
- Adherence to protocol requirements
- Completeness, quality, and analysis of measurements
- Amendments to the study protocol and consent forms
- Notification of and referral for abnormal findings
- Efficacy of the intervention at study termination (no interim analyses planned)

3 Organization and Interactions

Communication with DSMB members will be primarily through the DSMB executive liaison, [name], NIH Officer and the investigators at Virginia Commonwealth University (VCU). It is expected that study REDHART2 investigators will not communicate with DSMB members about the study directly, except when making

presentations or responding to questions at DSMB meetings or during conference calls.

a. DSMB Members and NHLBI Program Staff

DSMB members and their expertise are listed in Appendix A. Consistent with NHLBI policy, the DSMB is assigned an Executive Secretary (ES) to provide an unbiased staff interface for the DSMB, especially during executive sessions. The ES is responsible for assuring the accuracy and timely transmission of the final recommendations and DSMB minutes.

b. Scheduling, Timing, and Organization of Meetings

DSMB meetings will be held at the Virginia Commonwealth University, Richmond, VA, unless otherwise specified. For DSMB members residing outside of Virginia, telephone participation will be allowed for all meetings. The purpose of the first meeting is to review and discuss this Charter, to provide an overview of study REDHART2 activities, to review and make recommendations about the protocol(s), and to determine the frequency of interim analyses and whether data will or will not be masked to identity of randomized groups. Enrollment in a study cannot begin until the DSMB's recommendation for approval of the protocol has been made and IRB approval for the protocol including the DSMP has been obtained.

Meetings are held every 6 months, with additional meetings or conference calls scheduled as needed. Once the DSMB has established its working routine, consideration can be given to replacing one or both meeting per year with a conference call, if the agenda permits. Meetings and conference calls will be scheduled, and the agenda will be developed by the ES in close consultation with the Chair and the NHLBI Program Officer.

- For this DSMB, meetings will be held twice per year.
- The DSMB will monitor the progress of the present trial.
- No interim efficacy analyses are planned; however, an interim analysis could be performed at any time to assess efficacy and futility, if requested by the 3 or more members of the DSMB.
- The DSMB may choose to stop enrollment on the basis of safety data observed. If safety concerns are found, further enrollment will not be allowed until issues are resolved. If no safety concerns are found, enrollment will continue until the target sample size is reached.

The agenda for DSMB meetings and calls will be drafted by the ES in consultation with the Chair, investigators and the NHLBI Program Officer. The ES will finalize the agenda after consultation with the DSMB Chair. The agenda and meeting materials should be distributed by the ES 4 weeks before each meeting or call to the DSMB members, investigators, and the NHLBI Program Officer. The ES will collect and document all potential conflicts of interest from each member of the DSMB related to the design, conduct, interpretation, and publication of the study. Before each meeting, when the agenda is sent out, the ES will ask all DSMB members to state whether they have developed any new conflicts of interest since last meeting. This review will

be conducted in addition to the review for conflicts of interest conducted by the VCU IRB at the time of initial IRB approval. If a new conflict is reported, the Chair and staff will determine if the conflict limits the ability of the DSMB member to participate in the discussion. The DSMB also will review adverse event data, other safety data, quality and completeness of study data, and enrollment data at each meeting to ensure proper trial conduct.

It is expected that all DSMB members will attend every meeting and call. However, it is recognized that this may not always be possible. Quorum for voting is considered to be half the number of standing members plus one. The Board may wish to decide if particular expertise is needed within the quorum for the meeting to be valid. All standing Monitoring Board members are voting members. The Board may also wish to decide in advance whether *ad hoc* members can vote.

A quorum of this DSMB is considered to be 3 members out of total 5. Alternate members will be added to fill in cases in which the quorum of 3 cannot be achieved. All alternate members will receive equal vetting from the local IRB and from the Sponsor, NHLBI.

c. Discussion of Confidential Material

DSMB meetings and calls will be organized into open, closed, and executive sessions.

- During the **open sessions**, information will be presented to the DSMB by the Study Investigators and the NHLBI Program Staff as appropriate, with time for discussion.
- During the **closed sessions**, the DSMB will discuss confidential data from the study REDHART2, including information on efficacy and safety by treatment arm, if available. The DSMB will decide whether to remain masked to the treatment assignments at each meeting. If the closed session occurs on a conference call, steps will be taken to ensure that only the appropriate participants are on the call, and to invite others to re-join the call only at the conclusion of the closed session. NHLBI Program Officer would join the session only at the discretion of the Chair.

The DSMB may elect to hold an **executive session** in which only the DSMB members, NHLBI Program Officer (at the discretion of the Chair) and the ES are present in order to discuss study issues independently. Voting on recommendations will follow Roberts' Rules of Order (**Robert's Rules of Order Newly Revised (10th Edition) RONR** by Henry M. Robert III, William J. Evans (Editor), Daniel H. Honemann (Editor), Thomas J. Balch (Editor), Sarah Corbin Robert, Henry M. Robert III, General Henry M. Robert)

If the executive session occurs on a conference call, steps will be taken to ensure that only the appropriate participants are on the call, and to invite others to re-join the call only at the conclusion of the executive session.

At the conclusion of the closed and executive sessions, the participants will be re-

convened so that the DSMB Chair can provide a summary of the DSMB's recommendations. This provides an opportunity for study investigators and NHLBI Program Officer to ask questions to clarify the recommendations, if necessary. The meeting is then adjourned.

d. Reports of DSMB Deliberations

- Formal minutes: The ES is responsible for the accuracy and transmission of the formal DSMB minutes, within 14 days of each meeting or call. These minutes prepared to summarize the key points of the discussion and debate, requests for additional information, response of the investigators to previous recommendations, and the recommendations from the current meeting. Prior to submission to the investigators and the NHLBI Program Officer, minutes will be reviewed by the DSMB Chair for final review and approval. The DSMB Chair may sign the minutes or indicate approval electronically via email. Then, the minutes are sent to the investigators and the NHLBI Program Officer.
- Reports to IRBs: The investigators will prepare a memo documenting DSMB's deliberations and recommendations and send the memo to VCU IRB and NHLBI Program Officer.
- The DSMB report to the investigators will be forwarded to the NHLBI Program Officer, including the discussion of the concerns, and the basis for any recommendations that the DSMB has made in response to the concerns (within 7 calendar days if fatal or life-threatening unexpected, suspected serious adverse reactions; or within 14 days for unanticipated problem that is not an SAE or within 15 calendar days for all non-fatal, non-life threatening unexpected, suspected serious adverse reactions, or within 30 days of receipt of the DSMB or IRB report for all other unanticipated problems or scheduled meetings).

e. Reports to the DSMB

For each meeting, the investigators will prepare summary reports and tables to facilitate the oversight role of the DSMB. The DSMB should discuss at the first or subsequent meetings what data they wish to review and how it should be presented. The regular reports to the DSMB will contain blinded data for all enrolled subjects. If necessary, the DSMB may request un-blinding of the data, in which case, the DSMB will request that the randomization log be sent to the study biostatistician ([name]), who will then prepare an un-blinded report for the DSMB.

f. Statistical Monitoring Guidelines

A biostatistician will serve as a voting member of the DSMB. At the first meeting, review of the protocol will include review of the statistical analysis plan. The DSMB should discuss the adequacy of that plan. The final plan, whether part of a research protocol or separate document, will be maintained as an appendix to this charter. The DSMB should discuss the statistical monitoring procedures they propose to follow to guide their recommendations about termination or continuation of the trial (if applicable). These procedures could include guidelines for early termination for benefit, termination for futility, and termination for safety reasons (if applicable).

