Appendix: DSMB Charter**1) KEY PERSONNEL**

Please refer to the IRB Roster and Delegation Log for a complete personnel list

Name	Role	Institution/ Division
[name]/PhD	Medical Responsible PI	VCU, Cardiology
[name] [name]	Study Operation PI	VCU, School of Pharmacy
[name]	Clinical Trial Operations	VCU, Cardiology
[name]	CPX Core Lab	University of Illinois, Chicago
[name]	Investigational Pharmacy	VCU, School of Pharmacy
[name]	Biostatistician	VCU, Biostatistics
[name]	DSMB Chair	University of Florida, Cardiology
[name]	DMSB member	VCU, Infectious disease
[name]	DSMB member	Virginia Cardiovascular Specialists
[name]	DSMB member	VCU, Immunology
[name]	DSMB member	VCU, Biostatistics, CCTR
[name]	DSMB liaison	VCU, Pauley Heart Center

Abbreviations: DSMB=Data Safety Monitoring Board

2) PROTOCOL SUMMARY

Title: Interleukin-1 Blockade in Recently Decompensated Heart Failure

Population: 102 patients (age >21 years) with a clinical diagnosis of systolic heart failure, and recent (within 2 weeks of discharge) hospitalization for heart failure

Site(s): Virginia Commonwealth University, Richmond, VA

Study Duration: 40 months

Description: Phase II clinical trial of Anakinra (or Placebo) (2:1 allocation) for the treatment of patients with recently decompensated systolic (LVEF≤40%) heart failure and increased systemic inflammation (CRP>2 mg/L)

Objectives: To determine the effects of Anakinra (or Placebo) on peak of aerobic exercise capacity (peak VO₂) measured with a cardiopulmonary test after 24 weeks

[figure not shown]
Study Design: Single-center, randomized, double-blinded, placebo-controlled clinical trial with allocation to Anakinra 100 mg daily or placebo in 2:1 ratio for 24 weeks

Estimated Time to Complete Enrollment: 36 months

Estimated Time to:

- First patient in:** 6-12 months from funding
- Last patient in:** 34 months from first patient enrolled
- Last patient out:** 40 months from first patient enrolled

3) SCHEMATIC OF STUDY DESIGN

4) DESCRIPTION

The **REDHART2** (*RE*cently *D*ecompensated *H*eart failure *A*nakinra *R*esponse *T*rial 2) study is a phase II clinical trial of anakinra or placebo to improve aerobic exercise capacity in patients with recently decompensated systolic heart failure (HF).

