5.1 Primary Endpoint(s)

Placebo-corrected changes in peak VO₂ at CPX after 24 weeks of treatment will be considered the primary endpoint. This will compare patients treated with anakinra (N=68) vs placebo (N=34), and provide a randomized, double-blinded assessment of the effects of IL-1 blockade on aerobic exercise performance. The data will be collected and electronically transferred to the core laboratory at the University of Illinois, Chicago, IL ([name]).

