11.2 Sample Size Considerations

The sample size for this pilot study is calculated according to the primary endpoint of

difference in interval change in peak VO_2 at 24 weeks between anakinra and placebo. Given an expected average peak VO_2 of 15 mL/kg/min for HF patients, 68 subjects randomized to anakinra and 34 subjects randomized to placebo (2:1 randomization) would provide approximately >95% power to detect a difference of 1.6 $\text{mL}\cdot\text{kg}^{-1}\cdot\text{min}^{-1}$ (standard deviation of 1.7-2.0 $\text{mL}\cdot\text{kg}^{-1}\cdot\text{min}^{-1}$) in peak VO_2 on top of placebo. A conservative estimate of 20% loss to follow-up or withdrawal would retain >90% power.

		Effect size of treatment on top of placebo				
	$\text{mL}\cdot\text{kg}^{-1}\cdot\text{min}^{-1}$	+1.2	+1.4	+1.6	+2.4	+3.2
Standard Deviation	2.3	0.70	0.83	0.91	>0.99	>0.99
	2.0	0.82	0.92	0.97†	>0.99	>0.99
	1.7	0.92	0.98	0.99	>0.99	>0.99
	1.4	0.98	0.99	>0.99	>0.99	>0.99*

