11.3.2 Handling of Missing Data

Cases with missing data for all follow-up CPX at 6, 12 and 24 weeks will be omitted from the efficacy analysis due to inability to calculate the primary endpoint (change in peak VO_2). Considering that the main variable of interest (peak VO_2) is expected not to improve over time with placebo in patients with systolic HF and exclusion of patient with missing

data would inevitably lead to a survivorship bias, we will use the last observation carried forward (LOCF) method to impute the missing data at 12 and 24 weeks for the primary analysis. We will also perform the Little's Missing Completely At Random (MCAR) test to determine whether the appropriateness of imputing missing values and perform a Multivariate Imputation by Chained Equation (MICE) to validate the finding of peak VO₂ using a different method for data inference.

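### Under 2:1 allocation, the A/B coding in section 11.3.3 does not blind the primary analyst, because group size shows which arm is anakinra

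*Combined protocol and SAP*

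**What the plan says.** Section 11.3.3 sends the exercise-test data to the core laboratory and says of the analyst there that, after the database is locked, "he will be provided a group allocation according to treatment A or B (blinded to real treatment". It adds that "the description of the group allocation will be disclosed only after completion of the analysis".

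The allocation ratio is set in three places:
- Section 2 (Protocol Summary) describes "allocation to Anakinra 100 mg daily or placebo in 2:1 ratio for 24 weeks".
- Section 5.1 says of the primary endpoint: "This will compare patients treated with anakinra (N=68) vs placebo (N=34".
- Section 11.2 bases the sample size on "68 subjects randomized to anakinra and 34 subjects randomized to placebo (2:1 randomization".

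On missing data, section 11.3.2 says for the primary analysis that "we will use the last observation carried forward (LOCF) method". Section 11.3.3 ends with "All analyses will be based on a 'complete case' approach".

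No other device for hiding arm identity from the analyst is described, such as dummy codes or dividing the larger arm.

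**The concern.** Two-letter coding hides the arms only if nothing visible distinguishes the two groups. Under 2:1 allocation their sizes do. A tally of the code list shows one group about twice the other, and the protocol says which arm is the larger. The plan therefore states a property that its own design rules out, and a trial report repeating the statement would be inaccurate.

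What is at stake is narrow. Codes are released only after lock, so no outcome value can be changed in the light of the arm. What remains open is how the locked data are analysed, and the two sections on missing data do not agree on that.

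**Working it through.** **Inputs**
- Groups: 68 anakinra, 34 placebo, total 102 (sections 5.1 and 11.2).
- Difference 1.6, SD 1.7 to 2.0 mL/kg/min, 20% loss (section 11.2); two-sided 0.05 (section 11.3.3).
- Randomization by a pharmacy algorithm (section 7.2). Blocking is not described, so simple 2:1 randomization is taken as the worst case.
- Section 11.3.2 omits only patients with no follow-up exercise test at all.

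**Step 1. Reproduce the plan's figure, to confirm the 68/34 split.**
SE = SD × √(1/68 + 1/34) = 2.0 × 0.2100 = 0.420. Then 1.6/0.420 = 3.81, and power = Φ(3.81 − 1.96) = 0.968 (0.965 with the noncentral t). The table in section 11.2 gives 0.97, and the text says the sample "would provide approximately >95% power to detect a difference of 1.6". At SD 1.7 the result is 0.994 against 0.99 in the table. With 54 and 27 patients and SD 2.0 power is 0.92, which agrees with the stated retention of more than 90%. The split is the one the plan really uses.

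**Step 2. Sizes the analyst would see.**
- All randomized patients coded: 68 and 34, so 68/102 = 66.7% in one group.
- After 20% loss in each arm: 0.8 × 68 = 54.4 and 0.8 × 34 = 27.2, about 54 and 27.
- After 30% loss in anakinra only: 0.7 × 68 = 47.6, about 48 and 34.

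**Step 3. Chance that size misleads or fails to identify**, taken as the probability that the placebo group is at least as large as the anakinra group.

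Simple randomization: P(X ≥ N/2) with X ~ Binomial(N, 1/3).
- N = 102: 0.0004
- N = 40: 0.02
- N = 20: 0.09

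The smaller N are assumptions. They are shown because enrollment was halted in March 2020 before it was allowed to resume, so the final number could fall short.

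Fixed 68/34 with independent loss: Σ P(X = i) × P(Y ≥ i), with X ~ Binomial(68, 1 − anakinra loss) and Y ~ Binomial(34, 1 − placebo loss).

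| Loss, anakinra | Loss, placebo | Probability |
|---|---|---|
| 20% | 20% | about 1e-10 |
| 30% | 10% | 0.00005 |
| 30% | 0% | 0.0004 |
| 40% | 20% | 0.002 |
| 40% | 0% | 0.06 |
| 50% | 0% | 0.55 |

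Size ceases to be a reliable guide only under extreme differential loss. Even then, a code list covering everyone randomized would still show the original 68 and 34.

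**Step 4. What is still open when the codes arrive.** The model family, the two-sided 0.05 level and the definition of peak VO2 (section 7.4) are stated. The missing-data rule has two incompatible statements: LOCF in section 11.3.2 and complete cases in section 11.3.3.

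**The case against.** A reader might infer that failed masking is what allows the analyst to choose between LOCF and complete cases. The documents do not support that. The test is two-sided, and swapping the labels A and B reverses the sign of the difference but leaves the p-value unchanged. A properly masked analyst could run both rules and keep the smaller p-value; the labels add only the direction. The conflict between the two sections would exist under 1:1 allocation. This objection stands, and the conflict is treated here as a separate defect.

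A reader might also take A/B coding to be the plan's declared safeguard against result-driven choices. Section 11.3.3 gives the procedure and no purpose, so that reading is an inference. Nor is it right to say that the primary method is wholly open: section 11.3.2 names LOCF for the primary analysis, gives reasons, and adds multiple imputation as a check. Section 3.f of the DSMB charter also allows for a final statistical plan in a separate document. One that fixes these choices cannot be excluded, but none is among the documents available.

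Finally, the masking that protects the data is unaffected. The pharmacy restricts the randomization log, exercise data reach the core laboratory without identifiers, and echocardiogram readers and adjudicators are blinded. That stands, and it limits the point to one analyst after database lock. None of it rescues the statement that this analyst is blinded.

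**Conclusion.** The point holds in limited form. At the planned 68 and 34, and at about 54 and 27 after 20% loss, group size identifies anakinra for anyone who knows the ratio, so the stated masking does not exist. This assumes that the analyst knows the 2:1 ratio, which the protocol states openly, and that loss is not extremely unequal between arms.

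The exposure is confined to analytic choices after lock. Sample size and power do not change. The documents allow no estimate of any effect on the treatment difference or the type I error, and none is claimed. It would be wrong to conclude that the double-blind conduct of the trial or its outcome data are compromised. This is a modest defect, worth correcting because the statement is inaccurate and the correction is nearly free.

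**What to change.** Before any allocation codes are released:
1. State one missing-data rule for the primary analysis and make sections 11.3.2 and 11.3.3 agree on it.
2. Finalise the primary analysis program and sign it off with a date.
3. Remove from section 11.3.3 the statement that A/B coding blinds the analyst.

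These steps cost a short amendment and earlier programming.

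Optionally, the pharmacy can divide anakinra at random into two coded sets, so that three groups of about 34 are supplied, with treatment-revealing variables such as CRP withheld until sign-off. The signed-off program is then run once for each possible placebo group. The cost is a different code list and three runs of one program. This hides identity by size only. If the true difference were 1.6 with SD 2.0, placebo would differ from the combined anakinra sets by an expected 3.81 standard errors, so the outcome itself could show which group is placebo. It also puts three candidate results in view before the key is opened. The split therefore adds to the sign-off of the program and cannot replace it.
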